In September 2015, a new FDA-approved test became available at Beaumont, computed tomography-derived fractional flow reserve (CT-FFR, provided by HeartFlow, Inc.), that provides flow information directly from computational fluid dynamic analysis of CCTA images without further testing^{7- 15}. This analysis does not involve any additional imaging, contrast or medications. CT-FFR has been shown to be more accurate in predicting the presence of true ischemia on invasive fractional flow reserve testing in the invasive catheterization laboratory (CATH-FFR). Patients managed by CATH-FFR have been shown to have better outcomes than patients managed using visual inspection of CATH stenosis alone. The standard cutoff for an abnormal CATH-FFR and CT-FFR is the measurement of a blood pressure drop of $\geq 20\%$ (FFR ≤ 0.80) across a given stenosis.

For Beaumont ED patients, CT-FFR has been in use on a research basis since September, 2015, but is not considered standard of care. Since September 2015 we have conducted a study to analyze clinical outcomes after CT-FFR, (a sub-analysis of HIC #2016-157, the Beaumont CT Registry). We have collected, analyzed data and submitted for publication, data on 147 ED patients with CCTA stenosis of 25-99% managed with CT-FFR and followed for a minimum of 90 days. These data show no evidence to date of increased risk, but do show improved prediction of the need for revascularization using CT-FFR (see Appendix, submitted for publication).

The objective of the present trial is to evaluate the CATH rate and diagnostic effectiveness of CT-FFR as compared to a standard of care diagnostic strategy (SOC) in the management of ACP patients with intermediate-to-severe stenosis on CCTA.

Hypotheses:

Primary Hypothesis:

Cardiac Catheterization Rate: Use of CT-FFR will reduce the CATH rate in ACP patients with >50% stenosis on CCTA. There will be a pre-specified subset analysis of the Intermediate (51-70%) and Severe (71-90%) stenosis groups.

Secondary Hypotheses:

1. Diagnostic Effectiveness: CT-FFR results will more accurately triage patients to CATH compared to patients triaged by SOC. True flow-limiting coronary stenosis will be defined by CATH-FFR as the gold standard in patients undergoing CATH. Accurate triage will be calculated as the proportion of patients with correct triage to CATH based on CATH-FFR results:

CT-FFR group:

True positive case: CT-FFR positive and CATH-FFR positive

True negative case: CT-FFR negative and CATH-FFR negative

Proportion of correct CT-FFR triage = (True positive + True negative) / All CATH

SOC group:

True positive case: SOC chosen by attending physician for CATH confirmed by CATH-FFR. By definition, the clinicians' decision to CATH based on clinical evidence is considered an SOC positive case, there can be no SOC true negative cases that go to CATH.

Proportion of correct SOC triage = True positive / All CATH

2. Safety: Patients following CT-FFR-guided management will have similar MACE rates, including death, ACS and unanticipated late revascularization when compared to SOC-guided patients.

Methods

Study Population

The study population will be drawn from ED ACP who have already undergone CCTA for diagnosis, and have been found to have 50% or greater stenosis but less than 90% of at least one coronary branch. Two-hundred patients meeting entry criteria will be enrolled from a sample of ED ACP patients at Beaumont Hospital (Royal Oak). These patients will be randomized 1:1 using sealed envelopes provided by the study statistician, to either standard of care (SOC) or CT-FFR management. (See Figure 1. Study Diagram)

Inclusion Criteria

1. Emergency department or inpatients admitted through the ED with chest pain suspicious for ACS based on history and physical examination.
2. At least one biomarker (troponin) and electrocardiogram with no evidence of definite ACS.
3. A completed CCTA demonstrating $\geq 50\%$ but $< 90\%$ stenosis of at least one coronary artery branch.
4. CCTA test images with sufficient diagnostic quality for CT-FFR analysis.
5. Ability and willingness to provide informed consent.

Exclusion Criteria

- 1 Left main coronary stenosis of 50% or greater.
- 2 CCTA lesions demonstrating stenosis >90% ("subtotal"), or complex, high-risk plaque characteristics resulting in an a priori recommendation for triage to CATH by CCTA interpreting physician.
- 3 Attending physician a priori decision for CATH.
- 4 Prior coronary stent, coronary bypass or prior known myocardial infarction.
- 5 Clinical instability, such as hypotension, signs of shock, and/or unrelieved or accelerating chest pain.
- 6 Pregnancy

Obtaining Consent

Consent will be obtained by a co-investigator. Patients will have at least 20 minutes to consider whether they wish to consent.

Screening Log

A screening log will be maintained by research coordinators of all patients who were considered for enrollment and their demographics, clinical characteristics and the reason for their exclusion.

Sample Size

Our primary outcome is the CATH rate at 3 months. Based on our previous analyses from our IRB 2016-157 study (the FFR-ACP study), the SOC arm had a 89.5% CATH rate in the 71-99% stenosis group and 58.3% in the 51-70% stenosis group. With the 51-70% stenosis group having twice as many patients as the 71-99% group, we anticipate 68.7% of CATHs in all SOC controls. In our previous CT-FFR negative patients, there were 65.6% CATHs in the 71-99% stenosis group and 21.3% in the 51-70% stenosis group. Again with a 2 to 1 ratio, we anticipate an overall CATH rate of 36.1% in the FFR patients. Since these are estimates for the FFR group, we calculated several possibilities. All have 90% power with a significance level of 0.05%.

We determined a sample size of 87 patients per arm are needed to detect this difference. We intend to randomize 100 patients per arm to adjust for any lost to follow-up. We used PASS 15 Power Analysis and Sample Size Software (2017). NCSS, LLC. Kaysville, Utah, USA, ncss.com/software/pass.

Numeric Results for Testing Two Proportions using the Z-Test with Unpooled Variance

H0: P1 - P2 = 0. H1: P1 - P2 = D1 ≠ 0.

Target	Actual						
Diff							
Power	Power*	N1	N2	N	P1	P2	D1
Alpha							
0.90	0.90148	44	44	88	0.6870	0.3600	0.3270
0.0500							
0.90	0.90458	59	59	118	0.6870	0.4000	0.2870
0.0500							

0.90	0.90155	87	87	174	0.6870	0.4500	0.2370
0.0500							

* Power was computed using the normal approximation method.

Randomization

We intend to include 200 patients (100 per arm). Patients will be randomized in a 1:1 ratio to Standard of Care (SOC) or CT-FFR-guided management, in alternating block design to ensure equal groups periodically. The order of randomization will be generated using SAS for Windows 9.3, Cary, NC. Randomization envelopes will be generated by a Beaumont Research Biostatistician and will be opened in sequential order. Once the patient has met all the inclusion criteria, none of the exclusion criteria and has signed the informed consent, the next envelope will be opened which will contain a slip indicating the patients assigned study number and to which arm they are being randomized.

SOC Group Management

Attending physicians will dictate SOC management according to their own clinical judgment. This could include discharge without further testing, EKG-only stress testing, stress echocardiography, stress myocardial perfusion imaging, direct admission and further noninvasive testing or CATH. In addition to standard testing, a blinded CT-FFR will be obtained for post hoc analysis, but it will not be used for patient management. Image data from our CT workstation will be sent directly to HeartFlow, Inc. over a secure research transfer node.

If attending physicians decide that SOC Group patients should undergo CATH, the protocol will specify an invasive fractional flow reserve will be performed on all lesions over 30% stenosis severity, to confirm the presence or absence of flow-limiting stenosis. This may be waived without protocol deviation if deemed unsafe by the severity of stenosis or due to clinical circumstances, as documented in a completed Physician Study Questionnaire.

CT-FFR-Guided Group Management

Patients in this group will be triaged using CT-FFR. Image data from our CT workstation will be sent directly to HeartFlow, Inc. over a secure Priority (STAT) transfer node. Interpreting physician will categorize CT-FFR results as follows:

1. CT-FFR >0.80. All CT-FFR segmental values are >0.80, with no indication of flow limiting ischemia. A non-binding recommendation that the patient undergo an initial trial of medical therapy will be made by the interpreting co-investigator. Attending physicians will be asked to complete a study Physician Questionnaire to determine whether they followed this recommendation or not, and if not, why not.
2. CT-FFR 0.70-0.80. These will be reported as values in the abnormal range without specific recommendations about whether CATH should be performed. Attending physicians will decide triage in consideration with other clinical data. Attending physicians will be asked to complete a study Physician Questionnaire to determine what clinical factors influenced their triage decision.

3. CT-FFR <0.70. These are abnormal values that are will be reported as high-risk. A non-binding recommendation that the patient undergo CATH will be made by the interpreting co-investigator. Attending physicians will be asked to complete a study Physician Questionnaire to determine whether they followed this recommendation or not, and if not, why not.

If attending physicians decide that study patients should undergo CATH, the protocol will specify that CATH-FFR will be performed on all lesions over 30% stenosis severity, to confirm the presence or absence of flow-limiting stenosis prior to coronary intervention or triage to medical therapy. This may be waived without protocol deviation if deemed unsafe due to the severity of stenosis or due to other clinical circumstances, as documented on the Physician Study Questionnaire.

Clinical Follow-up

Patients will be followed at 1 month, 3 month and 1 year using a chart review and structured telephone interviews. Permission will be requested from patients for examination of outside medical records including office records and hospital records related to coronary artery disease.

Risks of the Study

Both the SOC and CT-FFR management strategies are currently used routinely at Beaumont Health, where ED patients' diagnostic strategy is selected according to the preference of their individual attending physician. There is no risk from the research study associated with CCTA testing, as patients will already have completed a clinically ordered CCTA test prior to their eligibility for the study.

Both SOC and CT-FFR Group patients will undergo CATH if indicated by the results of noninvasive evaluation by CT-FFR or SOC physicians' clinical judgment. Based on the baseline year prior to CT-FFR (Sept. 2014 – Aug. 2015), the CATH rate in SOC group patients was 58%. The CATH rate in CT-FFR patients during the previous research period (IRB #2016-157) from Sept. 2015 – Dec. 2016 was similar, at 79/147 patients, or 54%. Thus, the risk from the incidence of CATH was similar in the two groups. The study protocol does require CATH-FFR in patients undergoing CATH (unless there are no lesions >30%). There is a theoretical risk of rare (<1%) vascular injury due to the CATH-FFR catheter, however, CATH-FFR is a standard clinically recommended procedure prior to revascularization in CATH patients to insure accurate diagnosis of flow-limiting stenosis. If attending physicians believe there is a clinical reason that CATH-FFR should not be done, such as a lesion that is too severe, it may be omitted without protocol deviation, as long as the reason is documented in the Physician Study Questionnaire. The additional radiation risk added by CATH-FFR is estimated at <1 mSv, equivalent to <1 year of annual background radiation from environmental sources.

Risks Associated with Heart Catheterization and Invasive Fractional Flow Reserve

Common (more than 10%)

- warm feeling or flushed feeling during adenosine infusion (which is part of the FFR study)
- lightheadedness
- nausea
- pain
- discomfort
- bruising or bleeding where the catheter is inserted in the groin
- radiation equivalent to 3-5 years of natural background radiation

Rare (less than 1%)

- contrast (dye) allergy
- diaphoresis (temporary excessive sweating)
- atrioventricular block -impaired conduction of the impulse that regulates the heartbeat (from adenosine)
- contrast induced nephropathy (deterioration of kidney function due to contrast exposure)
- hives (for those allergic to contrast dye)
- thrombosis (blood clots resulting in reduced blood flow)
- artery dissection (damage to the artery wall)
- perforation (a hole in the artery)
- stroke
- myocardial infarction (heart attack)
- death

Internal Safety Monitoring Committee

An Internal Safety Monitoring Committee will conduct regularly scheduled reviews of the safety of patients. Two physicians and a statistician who are not co-investigators will be included. Members will monitor safety outcomes, enrollment and completeness of follow-up. The Committee will meet after the first 20 patients and after each 40 subsequent patients till the study is completed. Any MACE event or major adverse outcome will be reported immediately to the Committee. The results of all Committee meetings will be provided to the IRB.

Data Analysis

Descriptive statistics will be given for all variables collected including indications for the test, demographics, patient history, CTA tech information, details from the physicians reading form, and from the CT-FFR. Missing data will remain missing and will not be replaced by substitutions or interpolation. Categorical variables will be summarized as counts and percentages. All continuous variables will be

summarized as means+/- the standard deviation where normal or median and 25th, 75th percentiles if not normal. The minimum and maximum will also be provided.

Catheterization Rate: The primary outcome will be examined between the 2 randomization arms using Pearson's Chi-square test. The Odds ratio and 95% confidence interval will also be reported.

Diagnostic Effectiveness: The secondary outcome will be defined as the proportion of accurate triage using CATH-FFR as the gold standard among all patients triaged to CATH by each strategy.

The SOC group will be analyzed according to actual triage decisions, as well as the hypothetical results of triage using a blinded CT-FFR analysis collected on those patients. The accuracy of triage between these two methods will then be compared.

Safety: The secondary outcome will be safety, as defined by the incidence of death, ACS or late unscheduled revascularization in each group.

Additional data analysis:

The Total length of stay, with sub-analysis of ED and inpatient length of stay will be reported as medians, 25th and 75th percentiles and minimum to maximum. The 2 randomization arms will be examined for each of these using Wilcoxon rank sum tests.

The hospital admission rate, the proportion of patients going to CATH in either arm who are found to have significant coronary stenosis (>50 stenosis), proportion of patients going to CATH who have a positive invasive FFR, percentage of patients undergoing PCI or CABG within 3 months, secondary diagnostic testing during index visit or within 3 months follow-up, including: recurrent ED visits, inpatient admissions for suspected acute coronary syndromes and/or CATH, outpatient or inpatient evaluation with cardiac CCTA or stress testing, cardiac surgery or PCI and MACE events (including all cause death, acute myocardial infarction, acute coronary syndromes, unscheduled revascularization after index visit) will be examined between the 2 arms using Pearson's Chi-square test where appropriate (Expected frequency>5 in all cells), otherwise Fisher's Exact tests will be used. The Odds ratios and 95% confidence intervals will also be reported.

[figure not shown]
Estimated costs of care: including all estimated charges based on Beaumont hospital analysis multiplied by the standard Medicare cost/charge ratio will be reported as medians, 25th and 75th percentiles and minimum to maximum. The 2 randomization arms will be examined using Wilcoxon rank sum tests.

We may explore possible associations between patient characteristics demographics, prior history or testing indications and the randomization groups, safety outcomes,

or events using contingency table methods, t tests or Wilcoxon Rank Sum, as appropriate. Associations between radiation dose/efficiency and patient characteristics may be explored with nonparametric methods. We may also explore possible relationships between the CTA stenosis categories (0%, 1-49%, 50- 100%) and the CT-FFR final test results categories and CATH and revascularization results. The occurrence of clinical events recorded at the 3 month chart review and structured patient questionnaire will be related to the category of final noninvasive results (Normal, Probably Normal, Equivocal, Probably Abnormal and Abnormal) using methods for contingency tables which incorporate the natural ordering of test categories. Odds ratios (ORs) with associated 95% confidence intervals (CIs) may be shown relating the occurrence of safety outcomes to test response categories with the normal category as the reference point.

Analysis will be completed by a Beaumont Research Institute biostatistician using The SAS System for Windows version 9.3 (or higher).

Figure 1 - Study Diagram

[figure not shown]

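### Diagnostic effectiveness is scored on the CT-FFR reading in one arm and on the decision to catheterise in the other, so identical patients with identical decisions can score differently

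*Combined protocol and SAP*

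**What the plan says.** Secondary Hypotheses, item 1, makes a comparative claim: CT-FFR will triage patients to CATH more accurately than SOC, with CATH-FFR as the reference. It then gives each arm its own rule.

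- CT-FFR arm: "Proportion of correct CT-FFR triage = (True positive + True negative) / All CATH". A true negative (TN) is a catheterised patient who is negative on both CT-FFR and CATH-FFR.
- SOC arm: "Proportion of correct SOC triage = True positive / All CATH". The decision to catheterise is itself the positive call, so "there can be no SOC true negative cases that go to CATH".

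Other sections bear on the same endpoint:

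- **CT-FFR-Guided Group Management.** When all values exceed 0.80, the report carries "A non-binding recommendation that the patient undergo an initial trial of medical therapy". Between 0.70 and 0.80 it carries no recommendation on CATH.
- **The same section, on CATH-FFR.** "This may be waived without protocol deviation if deemed unsafe due to the severity of stenosis", or for other documented clinical circumstances. SOC Group Management has a matching waiver, and Risks of the Study adds that CATH-FFR is not required when no lesion exceeds 30%.
- **Data Analysis.** The denominator is described as the patients each strategy sent to CATH. No test is named for this endpoint, and missing values are to stay missing.
- **Additional data analysis.** The share of CATH patients with a positive invasive FFR is listed for comparison between arms, by chi-square or Fisher's exact test with odds ratio and confidence interval.

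**The concern.** The two rules score different objects. In the CT-FFR arm the object is the reading; in the SOC arm it is the decision. Take a catheterised patient whose CT-FFR and CATH-FFR are both negative. In the CT-FFR arm this counts as correct triage, although the patient had a CATH that found no flow limitation. In the SOC arm the same patient counts as incorrect. A catheterised patient with negative CT-FFR and positive CATH-FFR is scored the other way round: wrong in the CT-FFR arm, right in SOC.

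At stake is the first secondary hypothesis. It could appear supported, or be missed, because of the scoring rule and not because CT-FFR changed who goes to CATH.

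**Working it through.** **1. The plan's own figures.** The documents give no expected value, sample size or power for this endpoint. The Sample Size blends reproduce: (2 × 58.3 + 89.5) / 3 = 68.7% for SOC and (2 × 21.3 + 65.6) / 3 = 36.1% for CT-FFR. The unpooled two-proportion formula also returns the tabulated 44, 59 and 87 per arm. These concern the primary endpoint and are not in dispute. I use only the SOC rate: 68.7% of 100 patients is about 69 CATHs.

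**2. The identity.** Divide catheterised patients with a CATH-FFR value into TP, FP, FN and TN by CT-FFR reading against CATH-FFR.

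- CT-FFR rule: (TP + TN) / All.
- SOC rule on the same patients: every CATH-FFR-positive patient is a correct decision, so (TP + FN) / All.
- Difference: (TN − FN) / All.

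TP and FP patients score the same under both rules. Only catheterised CT-FFR-negative patients produce the gap.

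**3. Sign.** Three assumed cohorts of 60 CATHs:

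| TP, FP, FN, TN | CT-FFR rule | SOC rule | Gap |
|---|---|---|---|
| 28, 8, 4, 20 | 48/60 = 80.0% | 32/60 = 53.3% | +26.7 points |
| 30, 10, 10, 10 | 40/60 = 66.7% | 40/60 = 66.7% | 0 |
| 30, 15, 10, 5 | 35/60 = 58.3% | 40/60 = 66.7% | −8.3 points |

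Within each row the patients and decisions are the same.

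**4. An uninformative reading.** Let the reading be positive with probability p regardless of CATH-FFR, let it change no decision, and let a share y of CATHs be CATH-FFR positive.

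- CT-FFR score: p·y + (1 − p)(1 − y). SOC score: y.
- Difference: (1 − p)(1 − 2y). It is positive if y is below one half and negative if above.
- p = 0.5, y = 0.40: 0.5 × 0.20 = +10 points (50% against 40%).
- p = 0.5, y = 0.60: 0.5 × (−0.20) = −10 points (50% against 60%).

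By exact binomial enumeration of a two-sided 5% chi-square test with 69 CATHs per arm, the first case gives false superiority in 21.5% of trials and the second false inferiority in 21.5%. The nominal rate is 2.5% in each direction. With one common rule, the total two-sided rate in the same setting is 4.7%. The values of p and y and the choice of test are my assumptions.

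**5. Will there be CT-FFR-negative CATHs?** The recommendation is non-binding and covers only an initial trial of medical therapy, CATH is counted to 3 months, and the formula itself has a TN term. Sample Size also states: "In our previous CT-FFR negative patients, there were 65.6% CATHs in the 71-99% stenosis group and 21.3% in the 51-70% stenosis group". I give that sentence little weight, because the same rates are then used for the whole arm ("we anticipate an overall CATH rate of 36.1% in the FFR patients").

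**6. Denominator.** Secondary Hypotheses divides by all CATHs; Data Analysis divides by those a strategy sent to CATH. A CATH without a CATH-FFR value can be neither TP nor TN. Keeping missing values missing does not say whether that patient stays in the denominator.

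**The case against.** **The asymmetry is deliberate and disclosed.** Both rules can be read as (TP + TN) / All CATH, with TN equal to zero in SOC because the classifier there is the decision itself. The hypothesis speaks of CT-FFR results, so scoring the result follows its wording. This stands as a description. It also means that false superiority is false only with respect to the yield of the decision; on the plan's own quantity the difference is real. But the hypothesis compares arms on triage, and agreement of a test minus yield of a decision does not measure that.

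**Data Analysis may already cure it.** If the denominator holds only patients whom CT-FFR sent to CATH, those catheterised against the recommendation drop out, TN is empty, and both arms are scored on yield. That reading is possible but conflicts with the explicit TN term over all CATHs. It also leaves readings of 0.70 to 0.80 unassigned, since no recommendation is made there.

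**The common measure is already planned.** It is, with a test. As an additional analysis, however, it does not decide the named hypothesis.

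**Stronger readings that a reader might infer.** One is that the rule must favour CT-FFR. It does not: the gap reverses when FN exceeds TN. Another is that its size can be derived by setting the Sample Size CATH rates in CT-FFR-negative patients against the Appendix revascularisation rates. The documents do not support this. Revascularisation is not CATH-FFR, the stenosis bands differ slightly, and the Sample Size rates are labelled CT-FFR negative but applied to all CT-FFR patients. A third is that the within-SOC comparison with blinded CT-FFR is defective because it reduces to TN against FN. In a paired comparison concordant cells always cancel, and that contrast is the informative one.

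**Conclusion.** Wrong as written. The endpoint scores the CT-FFR reading in one arm and the CATH decision in the other, so the same patients and decisions differ by (TN − FN) / All CATH. This is algebra and needs no assumption. The gap favours CT-FFR if TN exceeds FN, SOC if FN exceeds TN, and is zero if they are equal.

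Neither size nor direction can be fixed, because no CATH-FFR results by CT-FFR category are given. The figures of ±10 points and about 22% false significance illustrate the mechanism under assumed inputs; they do not predict this trial's result. Confidence is high in the asymmetry and not in its impact.

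Two smaller gaps belong to the same endpoint: the unreconciled denominators, and the absence of a rule for CATHs without CATH-FFR. The primary CATH-rate comparison and its sample size are unaffected. This should be fixed before the secondary analysis is run.

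**What to change.** 1. **One formula.** Define the between-arm endpoint as CATH-FFR positive / patients with CATH in both arms. Use the chi-square or Fisher test already given under Additional data analysis, and align Secondary Hypotheses and Data Analysis to it.
2. **One rule for CATHs without CATH-FFR, the same in both arms.** The main analysis takes measured CATHs plus those with no lesion above 30%, counted as negative. State this as an exception to the missing-data sentence. Report waivers and reasons by arm. Add sensitivity analyses counting (a) waived-for-severity as positive and (b) all waived as negative, also as stated exceptions.
3. **A measure on all randomised patients.** The yield conditions on CATH, so also report CATH without flow-limiting stenosis / all randomised, by arm.
4. **Test accuracy kept separate.** Report TP + TN agreement of CT-FFR with CATH-FFR in both arms, as accuracy in catheterised patients only.
5. **Within SOC.** Report side by side the TN count (CATHs that CT-FFR would have avoided) and the FN count (flow-limiting disease it would have missed). Do not compare CT-FFR positive predictive value with SOC yield, which favours any better-than-chance test. With assumed sensitivity 0.20, specificity 0.90 and prevalence 0.60, the predictive value is 0.12 / (0.12 + 0.04) = 75% against a yield of 60%, although 80% of flow-limiting disease is missed.

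**Cost.** This needs wording changes and minor analysis work. No new data are needed, since waivers are already documented on the Physician Study Questionnaire. Waived CATHs leave the main analysis, so precision falls slightly. Any apparent CT-FFR advantage may be smaller, and the measure in item 3 partly overlaps the primary endpoint.

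### The safety hypothesis is that MACE rates are similar, but the only between-arm MACE analysis tests for a difference, and no analysis uses the 1-year follow-up

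*Combined protocol and SAP*

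**What the plan says.** - **Hypothesis** (Secondary Hypotheses, item 2, Safety): "Patients following CT-FFR-guided management will have similar MACE rates, including death, ACS and unanticipated late revascularization when compared to SOC-guided patients". No margin, reading rule or time point is given.
- **Outcome** (Data Analysis, Safety paragraph): safety is a secondary outcome, "as defined by the incidence of death, ACS or late unscheduled revascularization in each group". No test or window is given here.
- **Between-arm method** (Additional data analysis): MACE is the last item in a long list. It ends "unscheduled revascularization after index visit) will be examined between the 2 arms using Pearson's Chi-square test where appropriate", and continues "otherwise Fisher's Exact tests will be used. The Odds ratios and 95% confidence intervals will also be reported". The chi-square test applies when all expected counts exceed 5.
- **Time window**: the same list includes "secondary diagnostic testing during index visit or within 3 months follow-up, including: recurrent ED visits". MACE comes later in that run, so the 3-month phrase may or may not govern it. A later exploratory sentence says "The occurrence of clinical events recorded at the 3 month chart review and structured patient questionnaire will be related to the category" of the noninvasive result. That is a 3-month analysis, but by test category and not by randomised arm.
- **Follow-up** (Clinical Follow-up): "Patients will be followed at 1 month, 3 month and 1 year using a chart review and structured telephone interviews". The 1-year contact appears in no analysis.
- **Sizing** (Sample Size): "Our primary outcome is the CATH rate at 3 months". The 87 per arm, raised to 100 for losses, is derived for that outcome only.

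**The concern.** The hypothesis and the method point in different directions. The method asks whether the data contradict equal rates. The hypothesis asserts that the rates are close. Failing to contradict equality supports closeness only if a material excess would probably have been detected, and with rare events and about 100 patients per arm that need not be so.

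This matters because the trial aims to reduce catheterization. A lower CATH rate is worth having only alongside a credible statement about the events that deferral might cause, and the hypothesis itself names late revascularization. As written, the plan does not say how its MACE result bears on that question, and it leaves the longest follow-up unused.

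**Working it through.** **1. The plan's own figure.** Inputs from Sample Size: P1 = 0.687, P2 = 0.45, two-sided alpha 0.05, 90% power, unpooled z-test.

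n = [P1(1−P1) + P2(1−P2)] × (z0.975 + z0.90)² / (P1−P2)²
= (0.2150 + 0.2475) × (1.960 + 1.282)² / 0.237² = 86.5, so 87 per arm, as stated.

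The calculation is sound for CATH. No MACE rate enters it, so precision on MACE is whatever 100 per arm happens to give.

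**2. What the planned test detects.** The documents give no MACE rates, so those below are assumptions. Power is the sum, over all pairs of event counts (a, b), of Bin(a; n, p1) × Bin(b; n, p2) for the pairs that the plan's rule declares significant at two-sided 0.05. The rule is Pearson if all expected counts exceed 5, otherwise Fisher.

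| Assumed rates | Power, 100 per arm | Power, 87 per arm |
|---|---|---|
| 2% vs 4% | 5% | 3% |
| 2% vs 6% | 20% | 15% |
| 5% vs 10% | 27% | 22% |
| 10% vs 20% | 52% | 45% |
| 5% vs 15% | 68% | 61% |
| 10% vs 25% | 82% | 75% |

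At 100 per arm a true doubling is missed 95%, 73% and 48% of the time from 2%, 5% and 10%. Large excesses at higher rates are usually detected.

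**3. What a non-significant result leaves open.** The Newcombe interval for d = p1 − p2 uses the Wilson limits (l, u) of each arm:

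lower = d − √[(p1−l1)² + (u2−p2)²]; upper = d + √[(u1−p1)² + (p2−l2)²].

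For 6 vs 2 events in 100, the Wilson limits are 2.78% to 12.48% and 0.55% to 7.00%. So:

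lower = 4 − √(3.22² + 5.00²) = −1.9 points; upper = 4 + √(6.48² + 1.45²) = +10.6 points.

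| Events, CT-FFR vs SOC (100 each) | p | Risk difference, 95% CI (points) | Odds ratio, 95% CI |
|---|---|---|---|
| 6 vs 2 | 0.28 (Fisher) | −1.9 to +10.6 | 3.1 (0.62 to 15.9) |
| 10 vs 5 | 0.18 (Pearson) | −2.6 to +13.0 | 2.1 (0.69 to 6.4) |
| 3 vs 0 | 0.25 (Fisher) | −1.2 to +8.5 | infinite |
| 9 vs 2 | 0.03 (Pearson) | +0.5 to +14.4 | not needed here |

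The first two rows are non-significant yet leave open an excess of more than 10 points. The last row shows that the test can flag a strong imbalance.

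**4. Empty arms.** With the same true rate p in both arms, the chance that at least one arm has no events is 1 − [1 − (1−p)^100]². At 1%, 2% and 5% this is 60%, 25% and 1%. The sample odds ratio is then zero, infinite or undefined. The risk-difference interval can still be computed.

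**The case against.** The strongest reply is that this is a secondary outcome which need not be powered, and that its own paragraph is descriptive, giving incidence by group. The plan reports counts and percentages as well as an odds ratio with a 95% CI, so a reader could work out the risk difference. An Internal Safety Monitoring Committee with members who are not co-investigators receives every MACE immediately. All of this is true. It limits the size of the point, but none of it links the reported result to the stated hypothesis or assigns the 1-year data.

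The power figures rest on assumed rates, and the low-rate scenarios have no anchor in the documents. That is why a range is shown, including the 52% for a doubling from 10%. The proposed wording changes neither power nor precision. It changes how the result will be read.

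A reader might go further in four ways that the documents do not support.

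- **That the sponsor plans to call p > 0.05 similarity.** No section says so. The gap is that none rules it out.
- **That the MACE window is open to choice after the data are seen.** The primary outcome, the PCI/CABG item, the list that ends with MACE and the event analysis by test category all point to 3 months. That is the natural reading and needs only to be stated.
- **That the odds-ratio limit of 15.9, applied to a 2% SOC risk, implies an excess of about 22 points.** This treats the observed SOC risk as known, and the plan never proposes the conversion. It is no argument against reporting an odds ratio.
- **That the trial needs a non-inferiority margin or a larger sample.** It does not, provided safety is presented as estimation.

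**Conclusion.** The point holds. A declared hypothesis of similarity is paired with a test of difference that cannot support it, and the planned 1-year follow-up has no analysis. Under assumed rates of 2%, 5% and 10% with 100 per arm, the planned test detects a doubling with probability 5%, 27% and 52%, so a non-significant result says little about similarity across that range. The odds-ratio CI conveys part of the uncertainty but gives no usable estimate with an empty arm, which is likely only if MACE is rare. The missing 3-month label is minor. The primary analysis and its sample size are unaffected, so this should be corrected but does not threaten the trial's main result.

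**What to change.** Restate the safety objective as estimation.

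1. **One definition.** The hypothesis and Safety paragraph describe revascularization differently from the Additional data analysis list, and only that list names acute myocardial infarction. Use the list's four components in all three places: death from any cause, acute myocardial infarction, acute coronary syndrome, and unscheduled revascularization after the index visit.
2. **Estimate and times.** Suggested wording:

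> The CT-FFR minus SOC difference in the proportion of patients with MACE will be reported with a 95% CI suited to sparse events (e.g. Newcombe), at 3 months (main) and at 1 year (supporting). Patients will be analysed by randomised arm. The denominator will be patients whose MACE status is known at that time, and the number of unknown status will be shown for each arm. A non-significant test will not be read as similarity; the upper confidence limit is the largest excess not excluded.

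3. **Keep** the planned test and odds ratio as descriptive.

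The denominator has to be stated because Data Analysis leaves missing values missing and Sample Size allows for losses (100 randomised against 87 needed).

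The cost is a few sentences and two extra tables from follow-up already scheduled. No margin, extra patients or extra visits are needed. The downside is a more modest safety claim.
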